8.0 Study Endpoints

8.1 Describe the primary and secondary study endpoints.

Response:

The endpoints of this study are:

Primary Efficacy Endpoint:

• Comparison between lamotrigine and placebo groups of the reduction of Ménière's vertigo attacks from baseline

Secondary Efficacy Endpoints:

- Comparison between lamotrigine and placebo groups of vertigo attacks:
- Responder rate: Percentage of patients with > 50% reduction in vertigo attack frequency during treatment vs. baseline
- Vertigo attack free rate analysis: Length of vertigo attackfree intervals, number and percentage of vertigo attack-free days per 28 days period, number and percentage of patients who are vertigo attack-free during the double blind phase
- Comparison between lamotrigine and placebo groups of hearing loss:
- Analysis of audiograms between baseline and end of the study
- Comparison between lamotrigine and placebo groups of symptom severity:
- Ménière's Disease Patients-Oriented Severity Index (MDPOSI)
- Tinnitus Handicap Inventory (THI) questionnaire
- Clinical Global Impression-Severity & Change
- Comparison between lamotrigine and placebo groups of quality of life:
- Dizziness Handicap Inventory (DHI) questionnaire
- AAO-HNS Ménière's disease self-assessment

- Patient Health Questionnaire-9 (PHQ-9)
- Generalized Anxiety Disorder 7-item scale (GAD-7)

8.2 Describe any primary or secondary safety endpoints.

Response:

N/A – no such endpoints

9.0 **Procedures Involved**

9.1 Describe and explain the study design.

Response:

This is a randomized double-blind pilot proof-of-concept clinical trial. The principal investigator and all staff involved in clinic visits will remain blinded until the blind is scheduled to be broken or there is an emergency.

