11.0 Data Management

11.1 Describe the data analysis plan, including any statistical procedures.

Response: The primary response will be the number of vertigo attacks as measured at baseline and at the end of the study period. The secondary responses will include the percentage of vertigo free patients, audiograms, symptom severity scales and quality of life scales (listed in the Approach section). The analysis set will include all subjects who are randomized and receive at least one dose of the study medication or the placebo. Integer or continuous variables will be presented by their mean and median and their SD and IQR. Categorical variables will be summarized using counts and percentages. Demographic and baseline characteristics of the enrolled subjects will be summarized through descriptive statistics for continuous variables and through frequencies for categorical variables. Demographic and baseline characteristics of the intervention and placebo groups will be compared to assess for comparability. Continuous variables will be compared using Wilcoxon rank-sum test and categorical variables will be compared through Fisher's exact test. We will test for reduction in the Ménière's vertigo attacks from baseline through Wilcoxon's sign rank test and will compare the reduction between the two treatment groups using Wilcoxon rank-sum test. The tests will be two-tailed and the significance level will be set to 0.05. Additionally, we will perform statistical modeling of the number of vertigo attacks longitudinally through generalized linear mixed effects model using Poisson or Negative Binomial distribution as appropriate. Data analysis will be conducted using SAS (SAS Institute Inc., Cary, NC, USA) and R (http://www.r-project.org/). All data analyses will be performed by [name] of the SUNY UB Statistical Consultant Laboratory.

11.2 Provide a power analysis.

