Response: According to our preliminary data, the mean number of vertigo attacks after 3 months of treatment with Lamotrigine was 4.91 (SD=7.24), and we expect the mean number of vertigo attacks in the placebo group to be approximately 13. We assumed Negative Binomial distribution for the response, two-sided tests, level of significance 0.05 and considered various sample sizes, mean and variance of the number of attacks in the two groups. We calculated the associated power for comparison of the mean response between the two groups by utilizing Monte Carlo simulations and using Negative Binomial regression model with log link. Each simulation consisted of 1000 iterations and was conducted in R (http://www.r-project.org/). This analysis showed that a power above 80% can be obtained with a sample of 12 participants.

Table: Associated Power for Comparison of the Mean Response between Treatment Groups Calculated with Monte Carlo Simulations and Negative Binomial Regression Model with Log Link

Total N	Mean Number	Standard	Mean Number	α	Power
	of Attacks in	Deviation of	of Attacks in	level	
	Lamotrigine	the number of	Placebo group		
	group at the end	attacks	at the end of		
	of the study		the study		
12	5	7.24	13	0.05	57.6
12	5	6	13	0.05	60.6
12	5	4	13	0.05	86.6
12	6	6	13	0.05	58.2
12	6	4	13	0.05	83.5
14	5	7.24	13	0.05	60.7
14	5	6	13	0.05	70.1
14	5	4	13	0.05	92.8
20	5	7.24	13	0.05	67.6
20	5	4	13	0.05	97.6
20	5	7.24	12	0.05	60.4
20	5	4	12	0.05	94.5
20	6	7.24	12	0.05	48.8
20	6	4	12	0.05	91.9
34	5	7.24	13	0.05	82.2
34	5	6	13	0.05	92.5

Update on 6/4/2015:

As of 6/4/2015		
Expected N complete		
Complete		
Currently enrolled		
Potentially eligible, not enrolled		
Screened & eligible but declined participation in study		
Screened and ineligible		
Started study but dropped out		
TOTAL		

We engage in a multi-step process to reduce drop-outs, however, this is a very long study (6 months), and some drop-outs are to be expected. Thus far, we've had 2 participants drop out of the study and 8 have completed. Therefore, our dropout rate is 25%. To compensate for drop-outs, we request to increase our enrollment by 25%, rounded to the nearest whole number attain equal numbers in each group, for a total N of 16.

11.3 Describe the steps that will be taken secure the data (e.g., training, authorization of access, password protection, encryption, physical controls, certificates of confidentiality, and separation of identifiers and data) during storage, use, and transmission.

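### The stated power of above 80% at 12 participants belongs to a negative binomial comparison of end-of-study counts, not to the rank-sum test on reduction from baseline that tests the primary endpoint

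*Combined protocol and SAP*

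**What the plan says.** Section 8.1 gives the primary efficacy endpoint as "Comparison between lamotrigine and placebo groups of the reduction of Ménière's vertigo attacks from baseline". Section 11.1 adds that "The primary response will be the number of vertigo attacks as measured at baseline and at the end of the study period", and that the analysis "will compare the reduction between the two treatment groups using Wilcoxon rank-sum test", two-tailed at 0.05. No other between-group test is named for this endpoint. A count model appears only as a supplement: "Additionally, we will perform statistical modeling of the number of vertigo attacks longitudinally through generalized linear mixed effects model using Poisson or Negative Binomial distribution".

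Section 11.2 takes another route. It states "We assumed Negative Binomial distribution for the response, two-sided tests, level of significance 0.05" and describes the calculation as a "comparison of the mean response between the two groups by utilizing Monte Carlo simulations and using Negative Binomial regression model with log link". The table's columns are the mean number of attacks in each arm at the end of the study and one SD. There is no column for a baseline count or for the correlation between baseline and end. The section concludes that "a power above 80% can be obtained with a sample of 12 participants". The June 2015 update in 11.2 raises enrolment to 16 for drop-out and leaves the power calculation as it was.

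**The concern.** A power figure describes one test applied to one response. Here the simulated test is a negative binomial regression and the planned one is a rank-sum test; the simulated response is an end count and the planned one is a reduction. The second difference matters more. The variance of a reduction depends on how widely baseline counts vary and how closely they track end counts. Section 2.2 reports a wide baseline spread (mean 13.5, SD 12.5 over three months), and 11.2 does not use it.

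At stake is how a null result would be read. A non-significant rank-sum result in 12 completers would be set against a power of above 80% that was never shown for that test.

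**Working it through.** **Inputs from the documents.** End-of-study means 5 or 6 v 13, SD 7.24, 6 or 4, two-sided 0.05, N = 12 (11.2); 6 v 6, since 11.2 aims for equal groups; baseline mean 13.5, SD 12.5 (2.2); at least six attacks over qualification plus lead-in (9.1).

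**Assumed, because the documents do not give them.** Correlation between baseline and end of 0.3, 0.5 or 0.7; negative binomial counts joined by a Gaussian copula; reduction taken as absolute or percent. The dispersion parameter is θ = mean² / (SD² − mean). For example, the 5-attack arm at SD 7.24 has θ = 25 / (52.42 − 5) = 0.53.

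**Step 1: reproduce the table with its own method.** Two-group negative binomial regression, tabled SD in both arms, 20,000 runs per row.

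**Step 2: change only the test.** Exact rank-sum on the same end counts. With 4,000 runs the simulation SE is at most √(0.25/4000) = 0.8 points.

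| N = 12 row | Stated | Wald / likelihood ratio | Exact rank-sum, end counts |
|---|---|---|---|
| 5 v 13, SD 7.24 | 57.6 | 56.5 / 50.7 | about 53 |
| 5 v 13, SD 6 | 60.6 | 65.0 / 59.4 | about 60 |
| 5 v 13, SD 4 | 86.6 | 89.0 / 85.5 | about 83 |
| 6 v 13, SD 6 | 58.2 | 58.5 / 52.5 | about 49 |
| 6 v 13, SD 4 | 83.5 | 84.0 / 80.5 | about 74 |

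Every N = 12 row is matched within 2 points by one of the two regression tests, so the table is sound for what it computes. A continuity-corrected rank-sum test runs about 3 points below the exact one. Part of the regression's advantage comes from exceeding its level: with both means at 13, the Wald test rejects in about 6% of runs at SD 4 and about 10% at SD 6 or 7.24. The exact rank-sum test on reduction rejects in about 4.4% (SD 4 at both times, correlation 0.5).

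**Step 3: change the response to reduction.** The variance is SD_B² + SD_E² − 2ρ·SD_B·SD_E, and the arms differ by 13 − 5 = 8 attacks. As a guide, at ρ = 0.5:

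- SD 12.5 at baseline, 7.24 at end: 156.25 + 52.42 − 90.50 = 118.17, SD 10.9. The difference is 8/10.9 = 0.73 SD.
- SD 4 at both times: 16 + 16 − 16 = 16, SD 4. The difference is 8/4 = 2 SD.

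Simulated rank-sum power, 5 v 13 attacks, N = 12, correlation 0.3 to 0.7:

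| Baseline mean (SD), end SD | Absolute reduction | Percent reduction |
|---|---|---|
| 13.5 (12.5), 7.24 | about 20–36% | about 42–70% |
| Same, baselines truncated at six attacks, end means kept | about 22–38% | about 55–77% |
| 13 (7.24), 7.24; baseline assumed | 32, 42, 56% | not run |
| 13 (4), 4; baseline assumed | about 67–93% (exact: 71, 83, 95%) | about 79–96% |

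If 16 were analysed, absolute reduction at the preliminary SDs would give about 25–47%. The 16 is meant to leave 12 after the stated 25% drop-out: 16 × 0.75 = 12.

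**The case against.** Four points can be made for the plan.

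- **One row survives the change of test.** A reader might infer that no N = 12 row reaches 80% under a rank-sum test. That holds only with the continuity correction. The exact test, a natural choice at 6 v 6, gives about 83% for 5 v 13 at SD 4, and 11.1 does not say which version will be used.
- **The preliminary baseline is not the trial's baseline.** It comes from clinic patients with definite or probable disease, 27 of 48 with migraine (6 + 21). The trial requires definite unilateral disease and excludes migraine. In the fitted distribution about 30% of draws fall below six attacks. The objection is fair, but truncating at six moves absolute reduction only to about 22–38% and percent reduction to about 55–77%.
- **Power need not be low.** With an SD of about 4 at both times, the planned test can match or exceed the stated figure. This stands, and it is why the documents do not support saying that the primary test is underpowered whatever the inputs. Pairing a baseline SD of 12.5 with an end SD of 4 would give 23–34%, but nothing in the documents suggests such a collapse in spread in a placebo arm going from 13.5 to 13, so I set no weight on it.
- **This is a pilot.** The rank-sum test stays valid whatever its power, and conduct is unaffected. That lowers the severity, but the protocol still chose to claim a power figure.

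**Conclusion.** The point holds as a misalignment between the power calculation and the primary analysis, and should be fixed. Sections 8.1 and 11.1 together make the rank-sum test on reduction the only between-group test of the primary endpoint, although 11.1 does not label it primary. The power in 11.2 is for a different test on a different response. The supplementary mixed model does not close the gap, because it is longitudinal and is not the two-group regression that was simulated.

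Power for the primary test is therefore not established. With 12 analysed at the preliminary SDs, it is below 80% for absolute and percent reduction alike at assumed correlations of 0.3 to 0.7. It passes 80% if the SD is about 4 at both times and the correlation is high enough; no section supports a baseline SD that small. The statement about the preliminary SDs is confined to 12 analysed: with 16, percent reduction at a correlation of 0.7 can pass 80%.

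A reader might also infer an arithmetic error in the table. There is none of substance; it reproduces closely under its own method.

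**What to change.** Rerun the Monte Carlo in 11.2 with the rank-sum test of 11.1, and state:

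- whether the test is exact or asymptotic;
- whether reduction is absolute or percent, and which weeks form the baseline;
- a baseline distribution consistent with eligibility (at least six attacks), with SDs from about 4 to the preliminary 12.5;
- end SDs that include 7.24;
- correlations of 0.3, 0.5 and 0.7;
- results for 12 and for 16 participants.

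Replace the table and its closing sentence with the resulting range. The sample size, endpoint and conduct need not change. The cost is a few hours of programming and a stated power that is less favourable at the preliminary SDs.

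I would not align the two sections by promoting the negative binomial model to primary. Eight participants had completed by the June 2015 update, 9.2 unblinds a staff member at Visit 8, and the Wald test exceeds its nominal level at 6 v 6.

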Between January 2011 and November 2013, 48 patients in the Dent Dizziness and Balance Center were diagnosed with Ménière's disease and were prescribed lamotrigine as an off-label treatment. These patients were given a definitive or probable diagnosis based on the AAO-HNS 1995 criteria and had experienced at least three attacks in the three months prior to treatment. Almost all patients had been previously seen by ENT or other specialists and had tried conventional treatments like an improved life style, a low-sodium diet and diuretics. Some patients even attempted surgical treatments. Dosages varied from 50-300mg daily; most patients experienced a reduction of vertigo attacks during titration, but if another attack occurred the dose was increased further. We found that 13 of the 48 patients (27.1%) were also diagnosed with some form of anxiety, six individuals (12.5%) with only migraine and 21 individuals (43.8%) with an anxiety disorder and migraine. Out of these 48 individuals, ten were lost to follow-up and four patients had side effects like rash and had to discontinue the medication. After removing the above 14 patients, 94.1% (32/34) of remaining individuals reported improvement in symptoms, especially a reduction of Ménière's vertigo attacks. Furthermore, 50% (16/32) of improved patients experienced complete vertigo attack remission. Before initiation of lamotrigine therapy, 48 patients reported a mean of 13.5 (SD=12.5) vertigo attacks in the preceding three months (Figure 1). Thirty-five of the patients completed the initial follow-up and

reported a mean of 4.9 (SD=7.2) vertigo attacks in the three months after starting lamotrigine, *p<0.0001 (Wilcoxon signed rank test). Twenty-eight patients reported a mean of 2.5 (SD=5.5) vertigo attacks after completion of a three-month maintenance dose, *p<0.0001 (compared to before lamotrigine). Vertigo attack reduction and remission was not affected by migraine comorbidity.

2.3 Provide the scientific or scholarly background for, rationale for, and significance of the research based on the existing literature and how will it add to existing knowledge.

Response:

Please refer to 2.1

2.4 Include complete specific citations/references.

Response:

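### Section 11.2 claims power above 80% with 12 participants, but its own table gives 57.6% at the SD it cites; only SD 4, which has no stated basis, passes 80%

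*Combined protocol and SAP*

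**What the plan says.** Section 11.2 starts from preliminary lamotrigine data (mean 4.91 attacks, SD 7.24) and adds that "we expect the mean number of vertigo attacks in the placebo group to be approximately 13". It assumes negative binomial counts and a two-sided 0.05 level, and simulates 1000 trials per scenario, each analysed by negative binomial regression with log link. It concludes: "This analysis showed that a power above 80% can be obtained with a sample of 12 participants". A table of 16 scenarios follows, with one SD column that is not assigned to an arm.

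The June 2015 update in the same section raises enrolment to 16 to allow for drop-outs. Section 23.2 still states that 12 completers are needed.

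Section 2.2 supplies the only observed attack-count SDs. Before treatment, "48 patients reported a mean of 13.5 (SD=12.5) vertigo attacks in the preceding three months". In the three months after starting lamotrigine, 35 patients had a mean of 4.9 (SD 7.2). Later, "Twenty-eight patients reported a mean of 2.5 (SD=5.5) vertigo attacks after completion of a three-month maintenance dose".

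Section 8.1 makes the reduction from baseline the primary endpoint. Section 11.1 says the analysts "will compare the reduction between the two treatment groups using Wilcoxon rank-sum test". As an additional analysis, "we will perform statistical modeling of the number of vertigo attacks longitudinally through generalized linear mixed effects model".

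**The concern.** The power sentence is the stated statistical basis for 12 participants. A reader will take it to apply to the inputs just cited, yet the table row for those inputs says otherwise, and the SD that does support the sentence is neither named nor justified.

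At the cited SD the tabled test would miss a true 13 v 5 difference about 42% of the time (100 − 57.6 = 42.4), not under 20%. A null result could then be read as adequately powered evidence against benefit.

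There is a second gap. The tabled power belongs to a different outcome and a different test from the planned comparison of reductions, so the plan gives no power for that comparison.

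**Working it through.** **1. Reading the plan's table at 12 participants**

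| Means (lamotrigine v placebo) | SD | Power, % |
|---|---|---|
| 5 v 13 | 7.24 | 57.6 |
| 5 v 13 | 6 | 60.6 |
| 6 v 13 | 6 | 58.2 |
| 5 v 13 | 4 | 86.6 |
| 6 v 13 | 4 | 83.5 |

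The first row is the cited scenario with 4.91 rounded to 5. Its shortfall is at least 80 − 57.6 = 22.4 points. For 5 v 13 at SD 7.24, power is 60.7% at 14 participants, 67.6% at 20 and 82.2% at 34.

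**2. Reproducing the table**

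Assumptions: equal arms, and the single SD applied to both. For a negative binomial count, variance = μ + μ²/k, so k = μ²/(SD² − μ). At SD 7.24, k = 25/(52.42 − 5) = 0.53 on lamotrigine and 169/(52.42 − 13) = 4.29 on placebo. Each simulated trial was fitted by maximum likelihood with a common dispersion and log link, two-sided 0.05, 20,000 replicates (standard error at most 0.4 points). Section 11.2 names no test, so both usual ones are shown.

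| N | Means | SD | Plan | Wald | Likelihood ratio |
|---|---|---|---|---|---|
| 12 | 5 v 13 | 7.24 | 57.6 | 56.4 | 50.3 |
| 12 | 5 v 13 | 6 | 60.6 | 65.4 | 59.4 |
| 12 | 5 v 13 | 4 | 86.6 | 89.4 | 85.8 |
| 12 | 6 v 13 | 6 | 58.2 | 58.5 | 52.9 |
| 12 | 6 v 13 | 4 | 83.5 | 84.1 | 80.0 |
| 14 | 5 v 13 | 7.24 | 60.7 | 58.6 | 53.2 |
| 20 | 5 v 13 | 7.24 | 67.6 | 66.8 | 63.0 |
| 34 | 5 v 13 | 7.24 | 82.2 | 83.0 | 80.9 |

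The plan's 1000 iterations carry a standard error of about √(0.576 × 0.424/1000) = 1.6 points. Wald fits most rows but not 5 v 13 at SD 6 or SD 4 with 12 participants. Likelihood ratio fits those two but not the SD 7.24 row. The test used therefore cannot be identified. Neither test brings the SD 7.24 or SD 6 rows at 12 participants near 80%.

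A normal approximation gives the same picture. With 6 per arm, power ≈ Φ(8/(SD√(2/6)) − 1.96). At SD 7.24 this is Φ(1.914 − 1.96) = 48%; at SD 4 it is Φ(3.464 − 1.96) = 93%.

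**3. How demanding SD 4 is**

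Negative binomial variance must exceed the mean, so with a placebo mean of 13 the SD must exceed √13 = 3.6. SD 4 gives variance 16, barely above Poisson. The only observed SD near that mean is 12.5 (variance 156), in pre-treatment clinic patients.

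**4. Other scenarios with 12 participants, 5 v 13 (Wald / likelihood ratio)**

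- SD 5.5 in both arms, the smallest SD in section 2.2: 70% / 65%.
- Lamotrigine SD 7.24 with an assumed placebo SD of 12.5: 42% / 36%.
- SD 4.5 in both arms: 82% / 77%. Reaching 80% needs an SD of about 4.5 or less.

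**5. The increase to 16**

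The plan adds 25%: 12 × 1.25 = 15, made 16 for equal arms. With its quoted 25% drop-out, 16 × 0.75 = 12 complete; with 2 lost out of 10, 16 × 0.80 = 12.8. The increase restores about 12 completers. Even if all 16 completed, the table brackets power at SD 7.24 between 60.7% (14) and 67.6% (20).

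**6. The planned test**

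A rank-sum test on simulated end-of-study counts with 12 participants gives about 50% at SD 7.24 and 80% at SD 4, so changing the test does not rescue the sentence. This is still not the power for the reduction from baseline. That needs a baseline SD and a baseline-to-end correlation in the trial population, and the documents give no correlation.

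**The case against.** The sentence says the power can be obtained, after noting that several means and variances were considered. Two rows do pass 80%, and the contrary rows are printed beneath it. It is therefore literally true for SD 4, and the trial is a pilot. That stands, but the sentence does not state its condition and follows directly on SD 7.24. A pilot may be underpowered; it should not claim otherwise.

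The 4.91 (7.24) figure covers the three months after starting lamotrigine, so it includes titration. The closer analogue of the 12-week study period is 2.5 (SD 5.5). Keeping that mean and SD together (2.5 v 13, SD 5.5 in both arms) gives about 76–78% Wald and 75–76% likelihood ratio with 12 participants, and 84% / 82% if 16 completed. So the shortfall may be much smaller than 22 points under other inputs. But the plan did not use those inputs, and with 12 participants they still fall short of 80%. The 16 figure needs every enrolled participant to complete.

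The trial excludes migraine and requires unilateral definite disease, so its SD could be lower than in the clinic series. That is possible, but the documents do not argue it.

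Applying one SD to both arms is an inference from the single column. Equal SDs reproduce the table best, but the trial statistician should confirm it.

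The test mismatch is a separate point, and section 11.1 does include a count model, though only as an additional analysis of longitudinal counts.

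**Conclusion.** The concern holds. For the inputs section 11.2 cites, its own table gives 57.6%, not above 80%; this needs no recalculation. With 12 participants the claim is true only at SD 4, which has no stated basis and is below all three observed SDs. At SD 7.24 the table passes 80% only at 34 participants, and enrolling 16 does not close the gap.

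The simulations support this and rest on equal arms, negative binomial counts and an assumed placebo SD. For placebo the documents give an expected mean and no SD. The size of the shortfall depends on the inputs; its existence with 12 participants does not, across the scenarios based on SDs from the preliminary data.

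The tabled power is also not the power of the planned rank-sum comparison of reductions, which is unreported.

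**What to change.** Replace the power sentence in section 11.2 with wording such as:

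> With 12 participants, power is about 58% for 5 v 13 attacks with SD 7.24 in both arms (7.24 is the preliminary SD on lamotrigine and is assumed for placebo). In the table it exceeds 80% with 12 participants only at SD 4, an optimistic value below every SD in the preliminary data.

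The trial statistician should confirm that the SD column was applied to both arms.

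Add that the table applies to negative binomial regression of end-of-study counts. Add that power of the planned rank-sum test on the reduction depends on an assumed baseline SD and baseline-to-end correlation, shown as a labelled range produced by the trial statistician. The simulated figures given here are a check and should not go into the protocol.

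The cost is a wording change and a short power run, and the stated power becomes less favourable. The numbers (12 completers, 16 enrolled), the conduct and the analysis stay as they are.
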